# 1.0 Objectives

- 1. To determine the feasibility of acquiring *in-vivo* high-resolution microendoscopy (HRME) images of cervical adenocarcinoma *in situ* (AIS) immediately prior to conization.
- 2. To determine accuracy of HRME images in distinguishing AIS from normal cervical tissue.

# 2.0 Background

# Cervical adenocarcinoma in situ (AIS):

Cervical AIS is a precursor to invasive cervical adenocarcinoma, which accounts for approximately 25% of cervical cancers in the United States (1). While the incidence of squamous cell carcinoma of the cervix has been on the decline in the U.S. due to widespread screening, detection, and treatment of precancerous lesions, the incidence of both AIS and invasive cervical adenocarcinoma has been rising for unclear reasons (2). Similar to squamous cervical intraepithelial neoplasia (CIN) and squamous cell carcinoma, cervical AIS and invasive adenocarcinoma are caused by persistent cervical infections by carcinogenic or high-risk human papillomavirus (HPV). AIS is histologically characterized by atypical columnar epithelial cells with no invasion present. Unlike squamous CIN lesions, 10 to 13% of patients with AIS have multifocal disease, with foci of AIS separated by at least 2 mm of normal mucosa ("skip" lesions) (1,3-5).

The majority of patients are asymptomatic and the diagnosis of AIS is usually made following an abnormal Pap test. There are no clearly distinguishable clinical, cytological or colposcopic features of AIS. The lesion is usually located at the transformation zone with contiguous involvement of the endocervical canal (1,6). Cervical cytology and colposcopy-directed biopsy can miss up to 60% of AIS cases, however, the addition of endocervical curettage (ECC) significantly improves the detection rate (7). Cervical conization is usually required to make the diagnosis of AIS. Cold knife conization is preferred over loop electrosurgical excision procedure (LEEP) as it minimizes the risk of thermal artifact and allows the pathologist to determine the presence of invasive disease and margin status (8-10).

AlS is difficult to manage conservatively for several reasons. The lesion may be located high in the endocervical canal or be multicentric with "skip" lesions present. The sensitivity of cervical cytology and ECC is therefore only approximately 50%, making it difficult to adequately monitor women with AlS managed conservatively (4,11). In addition, the incidence of residual AlS or invasive adenocarcinoma following conization for AlS is high (3-5, 9, 12-14). Given these challenges, the standard treatment of AlS in women who have completed childbearing is simple hysterectomy. However, if the cervical cone margins are positive, a repeat cervical conization is performed prior to proceeding to simple hysterectomy to confirm negative margins and rule out an invasive occult cancer that could require different treatment. For women who desire future fertility, conservative management with cervical cone is an alternative provided the conization margins and ECC sample are negative. In women with a positive margin or ECC, repeat conization to remove the entire lesion and exclude the presence of invasive disease is recommended.

# High-Resolution Microendoscopy (HRME) Imaging:

The HRME imaging system is a low-cost, innovative cervical visualization technique to evaluate

epithelial cell morphology in situ. Proflavine, a topical contrast agent is applied to the cervix in a manner similar to the application of acetic acid at the time of colposcopy. The tip of a small fiber-optic probe is then placed directly onto the cervix, and the fluorescence from the proflavine-stained epithelium is immediately transmitted back to the HRME unit and displayed on a laptop computer, tablet or cell phone screen (Fig. Morphologic features typically evaluated by pathologists including nuclear crowding, pleomorphism, and nuclear-to-cytoplasm (N/C) ratio are assessed in vivo in real-time. Image analysis software is then used to quantify nuclear morphology parameters and calculate N/C ratio. This approach allows for real-time, point-of-care detection

**Fig. 1** (a) HRME system; (b) Proflavine is applied; (c) fiber optic probe; (d) high-resolution image is displayed on a laptop computer in real-time; (e) colposcopic view of lesion at 5:00, and (f) resulting HRME image. Histologic diagnosis was normal, consistent with the HRME image showing small, evenly spaced nuclei. (g) Colposcopic view of lesion at 1:00, and (f) resulting HRME image. Histologic diagnosis of this site was CIN3, consistent with the HRME image showing large, crowded, pleomorphic nuclei.

of high-grade precancerous cervical lesions without a biopsy being performed. The technique has been shown to be effective in the evaluation of squamous lesions and is being studied as part of a "See & Treat" approach in limited resource settings where patients can be screened and treated at the same visit with cryotherapy or LEEP.

# 3.0 Preliminary Data and Rationale

# Cervical adenocarcinoma in-situ (AIS):

Our group recently performed a large, retrospective study evaluating the outcomes of 188 patients with AIS (15). The mean age at diagnosis was 33.8 years (range 17.6-76.1), with many women of childbearing age. One hundred and seventy-two of the 180 women had at least one cone biopsy performed, with 110 (64.0%) undergoing a cold knife cone (CKC), and 62 (36.0%) undergoing a LEEP as their initial method of treatment. Positive margins were noted in 35.0% of patients undergoing CKC compared with 55.6% undergoing LEEP (p=0.017). Seventy-one patients ultimately underwent hysterectomy with residual disease noted in 10 patients (14.1%), 8 patients (11.3%) with residual AIS and 2 patients (2.8%) with invasive carcinoma. Of the 101 patients who did not undergo hysterectomy, 2 patients (2.0%) developed recurrent AIS at a median of 27.5 months (range 18- 37 months) from the last cone, and none developed invasive carcinoma. However, 28.6% of patients required more than one conization to achieve negative margins. The study concluded that conservative, fertility-sparing management of AIS with CKC alone is feasible but that two or more CKCs may be required to obtain negative margins.

# High-Resolution Microendoscopy (HRME) Imaging:

A pilot study evaluating HRME imaging for pre-invasive cervical neoplasia was recently

performed in 174 women in rural China (16). All patients underwent HPV testing, VIA, colposcopy and HRME imaging. Of the 69 women noted to have abnormalities on colposcopy, only 12 (17%) showed high-grade disease on biopsy. However, HRME imaging correctly classified all 12 high-grade areas (100%) as abnormal, and correctly classified 38 of the remaining 57 (67%) as normal. Furthermore, when patients were stratified based on a positive high-risk HPV DNA test, HRME imaging correctly identified 100% of the patients with CIN2 or greater. Of the 30 patients with a positive high-risk HPV DNA test but no histologic evidence of disease, only 6 patients (20%) were incorrectly identified as abnormal on HRME imaging. These preliminary data suggest that HRME has improved specificity over VIA and colposcopy, potentially leading to more accurate identification of patients needing treatment as part of a See & Treat protocol. Our collaborative group also recently completed a pilot study comparing HRME to colposcopy and biopsy in 60 patients with cervical dysplasia at Barretos Cancer Hospital in Brazil with final data analysis pending.

Our group is also evaluating HRME for use in conservative, fertility-sparing surgery for women with endometrial cancer. We are evaluating if HRME can help distinguish tumor margins in women undergoing resection of the endometrial tumor without hysterectomy. We recently completed a prospective pilot study evaluating the use of HRME in patients with endometrial cancer. Following hysterectomy, the uterus was examined *ex-vivo* to identify whether HRME could distinguish between tumor and normal endometrium following the application of proflavine. Preliminary results show a 74% concordance rate between HRME and final pathology, which is significantly higher than the 59% concordance rate between gross evaluation and final pathology. A prospective trial evaluating HRME *in-vivo* in women with endometrial cancer was recently approved and accrual will begin in the near future.

#### Rationale:

Cervical AIS is a significant pre-invasive disease that affects women of childbearing age. For women who desire future fertility, conservative management with cervical conization is considered a feasible option. However, the treatment is challenging as lesions are often located high in the endocervical canal, and are multicentric with "skip" lesions present. Repeat conizations must therefore be performed until negative margins are obtained. Given the microscopic nature of the disease, the surgeon typically cannot visually distinguish AIS from normal tissue in order to obtain negative margins. Furthermore, frozen section is difficult and inaccurate in assessing AIS margins. This lack of accurate intraoperative assessment results in 25-30% of patients undergoing one or more repeated conizations to obtain negative margins. In addition, an unnecessarily large specimen is sometimes removed in an attempt to be certain of obtaining negative margins. These large and repeat cervical conizations are known to be associated with adverse obstetrical outcomes, including preterm delivery and very low birth weight infants (17-19).

In order to overcome these challenges associated with the conservative management of AIS, we are proposing to use HRME, a novel cervical visualization technique, to evaluate epithelial cell morphology *in situ* in order to distinguish AIS from normal cervical tissue. *Our overall goal is to eventually use HRME to guide resection margins at the time of cervical conization for AIS*. Our *primary objective* is to determine the feasibility of acquiring *in-vivo* high-resolution microendoscopy (HRME) images of cervical adenocarcinoma *in situ* (AIS) immediately prior to conization. Our *secondary objective* is to determine accuracy of HRME images in distinguishing AIS from normal cervical tissue.

## 4.0 Eligibility Criteria

## Inclusion Criteria:

- 1. Any woman with a confirmed preoperative diagnosis of cervical AIS, including co-existing squamous CIN and/or microinvasive cancer
- 2. Women undergoing cold knife cone (CKC) of the cervix at MD Anderson
- 3. Negative pregnancy test for women of child-bearing potential
- 4. Women who are >/= 21 years of age and < 65 years of age
- 5. Ability to understand and the willingness to provide informed consent and sign a written Informed Consent Document (ICD)

## **Exclusion Criteria:**

- 1. Women < 21 years of age and >/= 65 years of age
- 2. Women with a known allergy to proflavine or acriflavine
- 3. Women who are pregnant or nursing
- 4. Patients unable or unwilling to provide informed consent or sign a written Informed Consent Document (ICD)

## **5.0 Pretreatment Evaluation/Obtaining Informed Consent:**

Patients will be screened for the study prior to surgery in the MD Anderson Cancer Center Colposcopy and Gynecologic Oncology clinics. All eligible patients will be approached by the PI or designee and offered participation in the study. Written informed consent will be obtained. The patient will be registered in the Clinical Oncology Research System (CORe). All patients will have their surgery performed at MD Anderson. Patients who are of child-bearing potential will have a pre-treatment pregnancy test (within 7 days) prior to surgery performed as part of their standard of care.

#### 6.0 Research Plan and Methods

#### Treatment Plan:

The patient will be taken to the operating room and per standard practice, prior to converting the surgical area to a sterile field, an exam under anesthesia will be performed. Five percent acetic acid will be applied to the cervix. Routine colposcopy with visual inspection of the cervix for aceto-whitening will be performed and the findings noted. This will be followed by the topical application of 0.01% proflavine solution to the cervix. The HRME probe will then be applied to areas of the cervix that appear to be both normal and abnormal. High-resolution images will be obtained and the findings noted. Lugol's solution may then be applied to the cervix per standard practice and the findings noted. This may be followed by re-application of 0.01% proflavine solution to the cervix. The HRME probe will then be applied to areas of the cervix that appear to be both normal and abnormal. High-resolution images will be obtained and the findings noted.

The patient and surgical area will then be prepped in the typical sterile fashion. A cold knife cone biopsy will then be performed per standard practice. The investigational procedures are anticipated to add approximately 10 minutes to the patient's time in the operating room.

Immediately following the CKC, the removed surgical specimen will be evaluated. Proflavine will be reapplied to the surgical specimen and repeat evaluation with HRME performed and high-resolution images obtained. Small ink dots will be placed on the tissue surface at each area that was noted to be abnormal as well as normal areas, to enable co-registration of image sites with subsequent histopathology sections. The specimen will then be submitted to pathology for the usual pathological analysis.

A member of the research team will contact each participant within 30 days of the procedure to ask how they are feeling and if they are experiencing any of the symptoms mentioned under the risks and side effects section of the informed consent.

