#### 10.0 Statistical Evaluation

We will enroll 20 patients in this exploratory study. We will first examine data from 5 patients to work out the logistical issues in the use of the imaging technology with the surgery as well as evaluation of safety. We will then examine data from the remaining patients in cohorts of 5. After each cohort of 5 patients we will review the logistics of the imaging technology and make adjustments deemed necessary to improve the surgical procedure. We will also evaluate safety.

Our primary objective is to determine the feasibility of acquiring *in-vivo* high-resolution microendoscopy (HRME) images of cervical adenocarcinoma in-situ (AIS) immediately prior to conization. We will use descriptive statistics to summarize the demographic and clinical characteristics of patients. We will estimate the proportion of patients for whom we can successfully acquire *in-vivo* HRME images of AIS immediately prior to conization with a 90% credible interval, assuming a beta(1.8, 0.2) prior distribution. This prior distribution is based on an anticipated success rate of 90%. If we complete the study with 18 patients for whom we can successfully acquire *in-vivo* HRME images of AIS, then our 90% credible interval will be 0.78 to 0.98. If we are able to successfully acquire in-vivo HRME images of at least 18 of the 20 patients enrolled in the study, then we will determine that the methodology is feasible.

Our secondary objective is to determine the accuracy of HRME images in distinguishing AIS from normal cervical tissue. We will tabulate AIS finding by the CKC specimen results as determined by pathology, and we will estimate the concordance of HRME images taken *ex-vivo* (as described in section 6.0) with pathology findings with a 90% credible, assuming a beta (1.8, 0.2) prior distribution for the concordance.

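### Accuracy pools all inked sites without fixing the epithelial type of the normal ones, so normal squamous tissue can stand in for the columnar tissue AIS must be told from, and could overstate accuracy at the margin

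*Combined protocol and SAP*

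**What the plan says.** Section 6.0 (Treatment Plan) has two rules for choosing sites. Before conization: "The HRME probe will then be applied to areas of the cervix that appear to be both normal and abnormal". On the excised cone, after proflavine is reapplied and imaging repeated: "Small ink dots will be placed on the tissue surface at each area that was noted to be abnormal as well as normal areas". The second rule matters here, because 10.0 takes accuracy from the ex-vivo images. Neither rule states the epithelial type, the position (ectocervix, transformation zone or canal), the distance from the lesion or the number of normal sites.

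Section 10.0 plans a cross-tabulation, "We will tabulate AIS finding by the CKC specimen results as determined by pathology", and a single concordance of the ex-vivo images, "as described in section 6.0) with pathology findings with a 90% credible, assuming a beta (1.8, 0.2) prior distribution for the concordance". It plans no separate sensitivity or specificity and no breakdown by epithelium. The data list in 6.0 includes HRME findings and final pathologic findings, but names no epithelial type per imaged site.

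The Background (2.0) and Rationale (3.0) say which tissue is at issue. On cell type: "AIS is histologically characterized by atypical columnar epithelial cells with no invasion present". On location: "The lesion is usually located at the transformation zone with contiguous involvement of the endocervical canal". On purpose: "Our overall goal is to eventually use HRME to guide resection margins at the time of cervical conization for AIS". On existing evidence for the device in the cervix: "The technique has been shown to be effective in the evaluation of squamous lesions".

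**The concern.** To find the edge of AIS in the transformation zone or canal, HRME must separate neoplastic columnar epithelium from the normal columnar epithelium beside it. Normal squamous epithelium differs from AIS in cell type as well as in the absence of neoplasia. A correct normal call on a squamous site may therefore show only that the device recognises squamous tissue. Under 10.0 that call counts as much as a correct call on columnar tissue.

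This is a spectrum effect in the negative sites: the pooled figure depends on a mix of tissue types that nobody has planned and the report need not show. A favourable concordance could then be carried forward to margin guidance although few or no normal columnar sites were tested. The cervical evidence cited concerns squamous lesions, so performance on normal cervical columnar tissue is the part about which least is known.

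**Working it through.** **The plan's own figure.** The documents give no design figure for accuracy. The only computed one is the feasibility interval at 18 of 20 successes. The posterior is Beta(1.8 + 18, 0.2 + 2) = Beta(19.8, 2.2), with 5% and 95% quantiles 0.780 and 0.979. This reproduces the stated 0.78 to 0.98, and the present point does not affect it.

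**Inputs.** From the documents: one overall concordance, ex-vivo inked sites, no rule on epithelial type. Not in the documents, so assumed:
- π, the share of sites that are AIS on pathology: 25% to 50%
- f, the squamous share of the normal sites: 0 to 1
- Se, the rate of correct calls on AIS sites: 0.80
- Sq and Col, the rates of correct normal calls on squamous and on columnar sites: varied below

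The inked site is taken as the unit, as co-registration by ink dot implies (10.0 does not name the unit), and every site is treated as AIS or normal.

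**Formula.** Concordance C = π·Se + (1 − π)·[f·Sq + (1 − f)·Col]. When the squamous share moves from f₀ to f₁, the change in C is (1 − π)·(f₁ − f₀)·(Sq − Col). Se cancels from the change.

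**Main illustration: Sq = 0.90, Col = 0.60, π = 0.50, Se = 0.80.**

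| Squamous share f | Pooled normal-call rate | Concordance |
|---|---|---|
| 0.2 | 0.2×0.90 + 0.8×0.60 = 0.66 | 0.5×0.80 + 0.5×0.66 = 0.73 |
| 0.5 | 0.5×0.90 + 0.5×0.60 = 0.75 | 0.5×0.80 + 0.5×0.75 = 0.775 |
| 0.8 | 0.8×0.90 + 0.2×0.60 = 0.84 | 0.5×0.80 + 0.5×0.84 = 0.82 |

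From f = 0.2 to f = 0.8 the normal-call rate rises by 18 points. Concordance, the planned endpoint, rises by 0.5 × 0.6 × 0.30 = 0.09, or 9 points.

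**Range, from all-columnar (f = 0) to all-squamous (f = 1) normals, Se = 0.80.**

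| Sq | Col | π | C at f = 0 | C at f = 1 | Change |
|---|---|---|---|---|---|
| 0.95 | 0.95 | 0.50 | 0.875 | 0.875 | 0 |
| 0.95 | 0.67 | 0.50 | 0.735 | 0.875 | +0.14 |
| 0.95 | 0.50 | 0.25 | 0.575 | 0.912 | about +0.34 |
| 0.67 | 0.95 | 0.50 | 0.875 | 0.735 | −0.14 |

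**Check against the cervical pilot in 3.0.** Its normal-call rates are 38/57 = 67% among colposcopically abnormal cases without high-grade disease, and (30 − 6)/30 = 80% among HPV-positive patients without histologic disease. Neither is split by epithelium, so neither estimates Sq or Col. Put in place of the assumed 90%, with Col still 60% and π = 0.50, they reduce the shift from f = 0.2 to f = 0.8 to 0.5 × 0.6 × 0.067 = 0.02 and 0.5 × 0.6 × 0.20 = 0.06.

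**The case against.** **The objective is met as worded.** Sections 1.0, 3.0 and 10.0 all speak of normal cervical tissue, and normal squamous cervix is that. Margin guidance is an eventual goal, not an objective of this 20-patient exploratory study. This stands. The problem is applicability to the next step, and it is no reason to replace the stated comparison.

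**Inflation is not shown.** A reader might infer that the concordance will be inflated. The documents do not support that: they give no performance by epithelial type, do not say which sites operators would favour on a cone, and leave open that columnar tissue is the easier one. This also stands. But the mix makes the pooled figure hard to interpret for margins whichever tissue is easier.

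**The in-vivo instruction does not govern accuracy.** A reader might take its wording to mean that any normal-looking cervix enters the endpoint. Only tissue on the excised cone can. The ink-dot sentence, however, leaves the same gap.

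**The information is partly recoverable.** Ink dots tie each image to a section, so pathology could label epithelial type afterwards, and 10.0 plans a tabulation as well as a concordance. That is right for sites that were inked. A normal columnar site that was never imaged and inked cannot be recovered.

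**Glandular tissue has been studied.** Section 3.0 reports 74% concordance in an ex-vivo endometrial pilot. This is relevant, but it concerns another organ and gives no specificity.

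**A columnar site may not always be available.** The documents do not establish that every cone has a normal-appearing columnar area that the probe can reach, so the requirement should apply only where one is present. Women with co-existing CIN are eligible (4.0), so the breakdown must also say how CIN sites are counted.

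**Conclusion.** The concern holds as a conditional one. Sections 6.0 and 10.0 together let normal squamous tissue form most or all of the normal comparator and then hide the mix in one figure, while 2.0 and 3.0 identify columnar tissue of the transformation zone and canal as what matters for the eventual use. The pooled concordance could therefore overstate performance at the columnar margin.

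The size rests wholly on assumed rates. It is 9 points of concordance for rates of 90% and 60%, half the sites AIS and a squamous share moving from 20% to 80%. Between all-columnar and all-squamous normals it runs from zero to about 34 points over the ranges tried where squamous is as easy or easier, and it is negative if columnar is easier. A reader might take the 18-point swing in the normal-call rate as the effect on the endpoint; it is not, because AIS sites dilute it. The feasibility objective and its interval are unaffected.

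**What to change.** In 6.0, add that at least one normal-appearing columnar site (canal or transformation zone) is imaged and inked ex vivo on each cone where one is present, and that squamous or columnar is recorded for every inked site from the histology section already cut. Add that field to the data list.

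In 10.0, keep the overall concordance. Add sensitivity and specificity separately, with specificity by epithelial type, prespecify AIS versus normal columnar as one comparison, and state where CIN sites are counted.

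The cost is a few sentences, one pathology field and a little more imaging of tissue already removed; nothing is added to the patient's procedure. The columnar comparison will be imprecise. One site per cone gives about 20, and 15 of 20 correct under the protocol's prior gives Beta(16.8, 5.2), a 90% interval of 0.60 to 0.89. The columnar figure may also be less favourable than the pooled one.
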